## 3 Study Design

### 3.1 General Design

**Study Overview.** Participants will be screened using a logistic risk stratification tool and will be enrolled if their probability of chronic pain is estimated to be  $\geq 0.3$ . Comprehensive phenotyping will be performed on enrolled patients and a plasma sample will be obtained. Randomization will occur and 15 patients will be treated with n-3 PUFAs, Vitamin D, n-3 PUFA+Vitamin D or placebo for 6). Each patient will be assessed at Week 6, Month 3, 6, and 12 following MThBI. Follow-up

telephone assessments will be completed by staff at the UNC Institute for Trauma Recovery. Safety will be assessed with weekly phone calls during the 6 week treatment period.

In this pilot randomized, double-blind study with 2x2 factorial design, eligible patients will be randomized across three sites to receive either n-3 PUFA supplementation, Vitamin D, n-3 PUFA + Vitamin D, or comparator lipid (soybean/corn oil) for 6 weeks following MThBI. Randomization will occur after the enrollment questionnaire within 72 hours of burn injury. Plasma, DNA, and RNA samples will be collected on study enrollment and at 6 weeks following MThBI. Follow-up assessments will be completed at 6 weeks, 3, 6 months and 1 year following MThBI.

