### **3.3 Primary Study Endpoints**

The primary endpoint of this study will examine the safety, feasibility and efficacy of n-3 PUFAs/Vitamin D to improve chronic pain outcomes following major thermal burn injury. **Outcome to assess safety:** Safety outcomes will be met after descriptive review of adverse outcomes, and comparison of adverse events is made across treatment groups by investigative team at the conclusion of the study. **Outcome to assess feasibility:** 60 patients will be enrolled, randomized into one of 4 treatment arms in a 1:1:1:1 ratio, and treated with study drug for 6 weeks following Major Thermal Burn injury severe enough to warrant surgery within a 24 month period. Proportion of participants completing following up at 6 weeks will be reported. The concentration of Vitamin D and n-3 PUFAs will be calculated before and after the 6 week treatment in each treatment arm to assess the response (expect an increase in both Vitamin D and n-3 PUFA in treatment arms). **Outcome to assess efficacy:** Efficacy of Vitamin D/PUFA will be measured by difference in pain severity in treatment arms versus control arms. We will 1) calculate a model estimated mean of chronic pain severity and corresponding 95% Confidence interval in each study group and 2) determine the slope of pain recovery among individuals treated with Vitamin D and n-3 PUFAs relative to control participants using a linear mixed model adjusting for sex, ethnicity, and study site.

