### **Subject Selection and Withdrawal**

### **3.6 Inclusion Criteria**

1.  $\geq 18$  years and  $\leq 65$  years of age
2. Enrollment procedures can feasibly be completed within 96 hours of thermal burn injury
3. Estimated TBSA  $\leq 30\%$
4. Surgical team has plans for surgical management of the burn wound (e.g. xenograft and/or autograft).
5. Patients experience a thermal burn injury, not an electrical or chemical burn.

6. Has a telephone to receive follow-up calls.
7. Able to speak and read English
8. Alert and oriented
9. Willing to take study medication for 6 weeks following enrollment
10. Subjects are capable of giving informed consent.
11. Predicted probability of chronic pain  $\geq 0.3$  when demographic parameters are entered into a logistic regression model developed from a previous cohort. (Initial pain score entered into this model will be based on the highest pain severity over the initial 24 hours after burn injury).
12. European American or African American

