Demographic and phenotypic data will be collected at this time. Patients will be asked to report demographic information including age, sex, ethnicity, education level, income level, and marital status. Pre-burn physiological traits will be assessed using pain catastrophizing, SF12 MCS, depression anxiety stress scale (DASS21), and Life events checklist. Characteristics of the patients' injuries will be reported through estimated percent total body surface area, mechanism their burn, and the donor/graft site location. Current pain at the graft site will be assessed using a 0-10 numeric rating scale, brief pain inventory, DN-4, S-LANSS and Regional Pain Scale (RPS). The patient's physical function will be assessed with the SF12 and a work/disabilities questionnaire. Depressive symptoms will be recorded using the DASS21. PTSD symptoms will be assessed with the PTSD Symptom Severity index-interview. Patient somatic symptoms will be recorded with the somatic symptoms inventory. The patient's burn wound will be documented with digital photos taken of the injury site. Dissociative symptoms will be documented with the Michigan Critical Events Perception Scale. Analgesic medication use will be recorded as daily milligram morphine equivalents. All patient information will be recorded by a trained research assistant or principal investigator. We additionally will assess treatment expectation using a modified survey that uses Likert scales prior randomization.

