**Primary study measures by timepoint.**

Domain	Measure	D1	6W	3M	6M	1Y
Demographic information	Age, sex, ethnicity, education level, income level, marital status	•				
Pre-burn psychological traits	Pain catastrophizing, SF12 MCS, DASS21, Life events checklist	•				
Burn Injury Characteristics	Estimated % TBSA, mechanism of burn, donor/graft site location	•				
Graft Site Pain severity	0-10 numeric rating scale; Brief Pain Inventory, DN-4, S-LANSS  †RPS	•	•	•	•	•
Physical function	SF12, work/disability questions	•	•	•	•	•
Depressive Symptoms	Depression anxiety stress scale (DASS21)	•	•	•	•	•
PTSD symptoms	PTSD Symptom Severity index-interview	•	•	•	•	•
Somatic Symptoms	Somatic symptoms inventory	•	•	•	•	•
Alcohol and drug use	TWEAK/SAOM		•	•		•
Burn wound evaluation	Digital photos of injury/wound site	•	•	•	•	•
Dissociative Symptoms	Michigan Critical Events Perception Scale	•				
Analgesic Medication Use	Daily milligram morphine equivalents, non-opioid analgesic use	•	•	•	•	•

†RPS = Regional pain scale, M=month, W=week, D= day, PTSD=post-traumatic stress disorder, TBSA: total body surface area, DN-4 Douleur Neuropathique 4, neuropathic pain questionnaire, S-LANSS: self report version of the Leeds Assessment of Neuropathic Pain scale SF-12: 12 item short form from the medical outcomes survey.

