**Efficacy:** Estimates of efficacy will be obtained via repeated measures analysis using mixed effects models (PROC MIXED in SAS 9.4). Prior to unblinding the data, our study statistician will perform a blind review of the data in which statistical models will be developed and tested using dummy (computer generated) treatment assignments. The goal of this is to fit the most appropriate model given aggregate data. Graft site pain severity will be collected in four waves across time; therefore, we will use mixed effects modeling with random error using an unstructured covariance matrix. The model will include fixed effects for PUFA, Vitamin D, their interaction, time, and the interactions between groups and time, as well as fixed effects for site, gender, and race/ethnicity. During blind review, competing nested fixed effect models will be compared. We will consider modeling time using either a) time as continuous variable with a linear model (i.e., slopes only), b) time as a continuous variable with a higher order polynomial model (up to cubic, given 4 time points), or c) time as a class variable. Competing fixed effect models will be fitted using maximum likelihood and compared using the BIC criterion. Once the form for the fixed effect model is selected, the final model will be fit using restricted maximum likelihood. After unblinding the data, we will use appropriately specified linear contrasts of the model parameters to estimate mean differences across groups at each time point along with 95% confidence intervals.

**Interim analysis:** Two interim analyses are planned after the enrollment of the 20th and 40th patients in the study. This will be conducted to ensure safety, perform a feasibility assessment, and assess potential efficacy. This optimizes study ethics, as it ensures safety of current and future study participants, allows

optimization of study protocol based on results of safety and feasibility assessment, and allows an efficacy assessment with appropriate statistical “penalty” for an interim look. Adverse events will be qualitatively reviewed at two interim analyses occurring after enrollment of the 20th patient and after enrollment of the 40th patient. While study investigators, staff, and participants remain blinded, the study statistician will prepare a qualitative summary of adverse events by type over the treatment groups. The results will be reported to investigators in aggregate such that blinding is maintained.

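### The efficacy model omits enrolment (D1) graft-site pain, which is collected; adjusting is cheap, but at the enrolled size it sharpens per-visit estimates only if D1 and later pain correlate above about 0.3

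*Combined protocol and SAP*

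**What the plan says.** Section 6.2 (Efficacy) gives the model fixed effects for PUFA, Vitamin D, their interaction and time, "and the interactions between groups and time, as well as fixed effects for site, gender, and race/ethnicity". Section 3.3 gives the same adjustment set for its efficacy outputs: "using a linear mixed model adjusting for sex, ethnicity, and study site". D1 pain appears in neither list.

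It is collected, however. Section 5.1 states: "Current pain at the graft site will be assessed using a 0-10 numeric rating scale". The table of primary study measures lists graft-site pain ("0-10 numeric rating scale; Brief Pain Inventory, DN-4, S-LANSS") at D1, week 6, months 3 and 6, and one year, which makes five time points.

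The model uses four: "Graft site pain severity will be collected in four waves across time". Section 3.1 lists exactly four follow-ups: "Each patient will be assessed at Week 6, Month 3, 6, and 12 following MThBI". The natural reading is that D1 pain is not an outcome wave either.

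Section 6.2 also plans a blind review in which "competing nested fixed effect models will be compared". The only choice it spells out is the form of time. Randomisation (4.3) is stratified on ethnicity and sex, not on pain.

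**The concern.** Sections 2 and 6.1 say that the efficacy estimates and their confidence intervals are meant to inform a larger trial. Section 6.2 records that enrolment ended at 24 of the planned 60, so those intervals will be wide. A baseline value of the outcome is an obvious candidate for gaining precision, and this one is already in hand. The plan does not say what to do with it.

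What is at stake is precision in the estimated mean differences at each visit. Section 2 makes efficacy a secondary objective, although 3.3 also names it within the primary endpoint.

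**Working it through.** **Inputs.** SD 2.6, two-sided 95% interval and up to 20% loss (6.1). Enrolled 24 (6.2), so about 24 × 0.8 = 19.2, taken as 19-20 completers. Three sites (3.1), four arms allocated 1:1:1:1 (3.3), strata of ethnicity and sex (4.3). Assumed: r from 0 to 0.5, equal expected site shares, and one third women and one third African American (3.8 targets 20 of each, out of 60).

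**The plan's own figure.** Section 6.1 states ±1.4 with 30 per comparison group and 20% loss. With 24 left per group, 1.96 × 2.6 × √(2/24) = 1.47, or 1.51 with a t quantile. With no loss, 1.96 × 2.6 × √(2/30) = 1.32. So ±1.4 does not reproduce exactly; nothing below depends on it.

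**Unadjusted width at 24.** For 12 against 12 in perfect balance, 1.96 × 2.6 × √(2/12) = 2.08. With 8 mean parameters (intercept, two main effects, interaction, two site terms, sex, race) and 24 − 8 = 16 degrees of freedom, the t-based value is about 2.25. Simulation with stratified permuted blocks, which allows for chance imbalance in the other covariates, gives about 2.40.

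**Effect of adjusting at one visit, with that visit's own D1 slope.** The expected ratio of adjusted to unadjusted half-width is √(1 − r²) × R0. R0 is the price of estimating one extra slope: the variance inflation from chance association between D1 pain and treatment, times the loss of one degree of freedom. R0 is 1.038 with 24 patients, 1.055 with 20 and 1.062 with 19. Break-even is r = √(1 − 1/R0²); for 24, √(1 − 1/1.038²) = 0.27.

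| Analysed | Unadjusted half-width | Ratio, r = 0 | r = 0.3 | r = 0.5 | Break-even r |
|---|---|---|---|---|---|
| 24 | 2.40 | 1.04 | 0.991 | 0.898 | 0.27 |
| 20 | 2.77 | 1.055 | 1.006 | 0.916 | 0.32 |
| 19 | 2.95 | 1.06 | 1.016 | 0.919 | 0.34 |

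The r = 0 and break-even columns follow the formula; the rest are from simulation, which agrees with it. In single simulated trials of 24, the adjusted interval was the narrower one in about 46% at r = 0.3 and 77% at r = 0.5. With 20 analysed, the shares were about 39% and 66%. At the planned size (48 completers) the ratios would be 1.014, 0.967 and 0.878.

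**Why r may be low.** D1 is current pain at a stage when "Surgical team has plans for surgical management of the burn wound", whereas follow-up (5.6) is average graft-site pain over 24 hours. Eligibility also uses a risk score that includes initial pain (3.6), which may restrict the range of D1 pain. If the D1 SD falls to a fraction u of its unselected value, r becomes ru/√(1 − r² + r²u²). With u = 0.8 or 0.6 (assumed), 0.5 becomes 0.42 or 0.33, and 0.3 becomes 0.24 or 0.185.

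**A slope common to all visits.** Two consequences follow.

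1. In any difference between visits, (Y_k − bX) − (Y_j − bX) = Y_k − Y_j. D1 pain (X) cancels, so group-by-time contrasts, including the slope of recovery in 3.3, are unchanged with complete data.
2. If r decays, one slope fits late visits badly. Assume r = 0.5, 0.4, 0.3 and 0.2 at the four visits, a between-visit correlation of 0.6, and equal SDs. The common standardised slope b is then 0.40. The residual SD ratio at visit k is √(1 − 2b·r_k + b²). Multiplied by about 1.039, this gives 0.91, 0.95, 1.00 and 1.04. The 12-month interval is about 4% wider. With its own slope it would be √(1 − 0.04) × 1.038 = 1.017, about 2% wider.

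**The case against.** The strongest reply is that this is a modelling preference, not a defect. Randomisation protects the unadjusted comparison, and its interval already reflects chance imbalance in D1 pain. No value of r is documented. At 19-20 completers adjustment loses on average at r = 0.3, and range restriction could bring even an unselected 0.5 down to about break-even. The 12-month interval may widen under a common slope, and one of the two efficacy outputs in 3.3 cannot gain from such a slope. The blind review could also admit a baseline term without any amendment.

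Most of this stands, and it limits the point to an optional improvement. It does not remove it: the review is not told to consider D1 pain, and saying in advance how a collected baseline outcome will be used costs almost nothing. Fitting the term would also estimate its association with later pain, which a larger trial needs to plan its analysis.

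A reader might infer that the omission biases the treatment comparison, or that adjustment would reliably tighten the intervals. The documents support neither: allocation is randomised, and no correlation is given. Nor do they show that baseline adjustment was ruled out, since the comparison of fixed-effect models leaves room for it.

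**Conclusion.** The point holds as a low-cost suggestion. D1 graft-site pain is collected and has no stated role in the efficacy analysis. Its use could narrow the per-visit intervals by about 8-10% if r is 0.5, would change them by 1-2% in either direction if r is 0.3, and would widen them by about 4-6% if r is 0. Break-even is about 0.27 with 24 analysed and 0.32-0.34 with 19-20. Net benefit at 19-24 patients is possible, not assured.

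These sizes rest on assumed values of r, on a single-visit approximation to the four-visit model, and on reading the four waves as the four follow-ups. The benefit is claimed for mean differences at each visit only, not for the slope of recovery under a common D1 slope.

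**What to change.** The documents do not say whether the arms have been unblinded since enrolment ended, so the change depends on that.

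- **If still blinded:** add D1 graft-site pain (0-10 scale) to the covariate lists in 6.2 and 3.3 as a prespecified term, dated as added after early termination. Use the blind review already planned in 6.2, on pooled data with dummy assignments, to choose between one slope common to all visits and a D1-by-time slope.
- **If unblinded:** keep the planned model and report the D1-adjusted model beside it as a labelled sensitivity analysis.

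Either way, state that a common D1 slope leaves the slope-of-recovery contrasts unchanged.

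The cost is a short addition to the analysis plan, no new data, and one degree of freedom per slope. The downside is intervals about 4-6% wider if D1 pain turns out to be unrelated to later pain.

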### 7.5 Stopping Rules

The entire trial will stop if any investigator judges it necessary for medical, safety, regulatory, or other reasons consistent with applicable laws, regulations, or good clinical practice.

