### 7.6 Medical Monitoring

**A. Safety Monitoring Plan:** Overall safety oversight will be the responsibility of the data coordinating center PI (DCC PI). Monitoring the study (across one or more study sites) is considerably facilitated by the use of a single electronic database

which can be reviewed by the network PI, study site PI(s), and other investigators. The DCC PI will monitor for adverse events that change study risk level and this will be communicated with the independent medical monitor if needed. Adverse events at individual study sites will also be monitored by the site PI. If an

Serious AE	Death Life threatening reaction Inpatient hospitalization prolonged, or rehospitalization Persistent or significant disability/incapacity Congenital anomaly/birth defect Represents other significant hazards or potentially serious harm to research subjects (similar to "important medical event")
Expected AE	Known potential effect of the drug (based on drug description information from manufacturer) or disease process

adverse event occurs which changes the study risk level, the DCC PI will immediately report this event to the DCC IRB (UNC IRB), inform the site PI(s), and oversee the process of modifying the study at the study site(s) as appropriate to address the change in risk. The DCC PI will also provide annual reports summarizing AE data to the data coordinating center IRB (UNC IRB) and any other requesting IRB. The site PI(s) will oversee patient safety at their site, with delegation of responsibilities to other investigators and designated study personnel as appropriate. The DCC PI, together with their study site teams, will ensure that all entry criteria are met prior to the initiation of the protocol, and that all study procedures and reporting of adverse events are performed according to the protocol. Serious adverse events (SAE's) will be monitored by the study site investigative teams in real time throughout the trial.

**Patient monitoring:** An adverse event is any physical or clinical change experienced by the patient. This includes the onset of new symptoms and the exacerbation of pre-existing conditions. Adverse event assessments will be performed according to the following schedule:

**Adverse event monitoring after discharge:** Adverse events will be assessed at each patient contact (telephone or text-messaged/mailed survey), which will occur weekly while on the study drug.

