Appendix 2 describes the adverse event grading scale and management guidelines for potential adverse events related to the study drugs. This chart covers a number of common adverse effects, but will not be comprehensive. As other situations are encountered and managed by the study team, this decision rule chart will be updated and expanded so that it remains current and inclusive.

Summary information regarding adverse events will be provided to the IRB at the time of annual IRB renewal. As described below, medical monitor reports will also be submitted to the UNC IRB on a quarterly basis. Criteria for stopping the study trial among all participants for review are shown in Appendix 2.

Patients experiencing adverse effects that in the opinion of the investigators merit drug dosage adjustment will have their dosage advanced more slowly, or the next dose reduced or held as appropriate. If necessary, patients will be maintained on a lower dose, or their dose will be re-advanced depending on the nature of the side effect(s). Patients who decline further participation and patients experiencing adverse effects that in the opinion of study investigators indicate that study drug should be stopped will be discontinued or tapered from study medication.

**Independent Medical Monitor:** To handle individual problems that may require communication directly with physician caring for the patient, or if decision making involves altering the study drug administration on a patient level, an independent Medical Monitor will become involved. This is to avoid any conflicts of interest that may arise. Data Handling and Record Keeping

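### As designed, the interim safety review cannot show an excess of adverse events in one arm, because no one with stated authority is sent events by arm

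*Combined protocol and SAP*

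**What the plan says.** Section 6.2 (Interim analysis) states: "Two interim analyses are planned after the enrollment of the 20th and 40th patients in the study". Among the reasons given is that "it ensures safety of current and future study participants". For safety, "the study statistician will prepare a qualitative summary of adverse events by type over the treatment groups", while investigators, staff and participants stay blinded. The next sentence sets what is passed on: "The results will be reported to investigators in aggregate such that blinding is maintained".

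On stopping, section 7.5 states: "The entire trial will stop if any investigator judges it necessary for medical, safety, regulatory, or other reasons". The adverse event table in section 14.1 repeats this rule.

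Section 7.6 places overall safety oversight with the principal investigator of the data coordinating center (DCC PI). It introduces the independent medical monitor with the words "To handle individual problems that may require communication directly with physician caring for the patient", and for decisions on study drug in a single patient. It also has the DCC PI pass adverse events that change the study's risk level to the monitor if needed, and adds that "medical monitor reports will also be submitted to the UNC IRB on a quarterly basis". The content of those reports, and whether they are split by arm, is not stated.

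Section 3.3 has the investigative team compare adverse events across treatment groups when the study concludes.

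**The concern.** Safety is part of the primary objective (section 2), and section 6.2 asks about both treatments and their combination. The question at an interim look is thus whether one drug, or the pair, brings more events than its comparator. An aggregate summary does not hold that information.

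The setting makes this matter. Section 1.5 names increased bleeding as a possible effect of the n-3 product, and section 3.6 requires planned surgical management of the burn. Bleeding can come from either source. The documents give no expected background rate against which a pooled count could be judged.

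If an excess arose in one arm, the plan gives no route by which someone able to act would see it before the end of the study.

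**Working it through.** No sample size, power or alpha figure in the plan bears on this point. The stopping boundaries in section 6.2 (3.428, 2.431 and 1.985) concern efficacy, and there is no safety boundary to reproduce. The check is a trace of who sees what, followed by an illustration.

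**Who sees what at an interim look**

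- *Investigators, including the DCC PI:* aggregate results with the blind kept (6.2). They hold the stated stopping power (7.5, 14.1) and, in the DCC PI's case, safety oversight (7.6).
- *Independent medical monitor:* individual problems, and study-level risk changes passed on by the DCC PI if needed (7.6). The monitor is not said to receive the interim summary or by-arm data, or to recommend on the trial as a whole. What reaches the monitor comes from a DCC PI who is blinded.
- *IRB:* risk-change reports, annual summaries and quarterly monitor reports (7.3.2, 7.6). None is described as by arm.
- *Study statistician:* prepares the summary over the treatment groups (6.2). No duty to raise an alarm, and no authority, is written. Section 4.3 says that the statistician is unblinded, and also that treatment identity reaches the statistician only when the study ends. If the second statement governs, it is unclear that anyone could produce a by-arm table at the look. The interim efficacy test in 6.2 needs group assignments too, so the two statements must be reconciled in any case.

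**Illustration (all counts and event rates are assumptions)**

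Allocation is 1:1:1:1, so balanced arms at the first look give 20/4 = 5 patients per arm and 10 v 10 for each factor.

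1. Suppose that 5 of the 20 have an event. The pooled figure is 5/20 = 25% for every split.
   - Split 5 v 0: two-sided Fisher p = 2 × C(10,5)/C(20,5) = 2 × 252/15504 = 0.0325.
   - Split 3 v 2: p = 1.00, since no other split is more probable.
2. Other totals behave in the same way. With 6 of 20, 3 v 3 gives p = 1.00 and 6 v 0 gives p = 0.011. With 8 of 40 (20 v 20), 4 v 4 gives p = 1.00 and 8 v 0 gives p = 0.003.

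The pooled report is the same in each pair, so it cannot tell the two situations apart.

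**What by-arm data could show**

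The probability of Fisher p ≤ 0.05 with more events on treatment is the sum of Bin(x; n, p0) × Bin(y; n, p1) over outcomes with y > x and p ≤ 0.05. The assumed control rate p0 is 10%.

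| Rate on treatment | 10 v 10 (look 1, by factor) | 20 v 20 (look 2, by factor) | 5 v 5 (look 1, two single arms) |
|---|---|---|---|
| 30% | 6% | 24% | 2% |
| 50% | 30% | 74% | 12% |
| 70% | 67% | 98% | 37% |

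In pooled form at look 1, the expected number of patients with an event is 10 × (0.10 + 0.30) = 4, and likewise 6 or 8, against 20 × 0.10 = 2 with no excess. A large rise might attract notice, but the documents give no reference rate and the total does not say where the rise lies.

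**The case against.** The strongest reply is that the look is not the only safeguard. Site teams follow serious events in real time and adverse events are sought weekly during treatment (7.6). Bleeding is assessed at 3 and 6 weeks (5.4, 5.5). Events are graded for relatedness, with rules for individual patients (14.1), and emergency unblinding exists (7.4). This stands: a reader might infer that the plan cannot detect harm at all, and the documents do not support that. A striking event type or a high total could surface through these routes. None of them compares arms.

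A reader might also infer that only investigators may stop the trial, or that the monitor deals solely with single patients. Section 7.5 says that any investigator may stop the trial, not that nobody else may. Section 7.6 gives the monitor a conditional study-level link and mentions quarterly reports. What stands is narrower: no one else is given stopping power in writing, and by-arm interim data are assigned to no one with authority.

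The word aggregate could mean masked group totals. The text does not say so, and its stress on keeping the blind makes pooling the more natural reading. If coded groups were meant, one sentence would settle it.

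The table above also shows how weak a by-arm comparison would be at 20 patients, and section 6.2 itself rules out inferential comparison of adverse events. That is a reason to have an experienced reader weigh the split, not a reason to withhold it.

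Lastly, section 6.2 records that enrollment ended after the 24th patient with one look held. No further enrollment-triggered look remains in this trial, which limits the practical effect of a change here.

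**Conclusion.** The point holds as a gap in design. If the plan is followed as written, the interim review cannot show an excess of events in one arm or in the combination, because those with the stated stopping power see results in aggregate and no section gives an unblinded reviewer with authority the by-arm figures. This rests on reading aggregate as pooled over arms, and on the absence of any other by-arm route in the documents.

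The loss of information is complete for the between-arm question: any split of a given total gives the same pooled report. The practical loss at the first look is smaller, since 10 v 10 would carry only a sparse signal.

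A reader might conclude that harm was missed in this trial, or that nobody saw events by arm. The documents support neither. They contain no adverse event results, and they do not say what was reviewed at the look that took place. For this trial, the point limits how that look may be described. For the larger trial that section 2 names as the long-term aim, it is a gap not to carry forward.

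**What to change.** - In sections 6.2 and 7.6, have the statistician send an adverse event table by arm, with arms coded, to the existing independent medical monitor at each interim look. The monitor returns a written recommendation on the trial to the DCC PI. Investigators keep the aggregate table. The review is by judgement, with no test.
- In section 4.3, reconcile the two statements on when the statistician holds the treatment codes, and make 6.2 agree.
- In section 6.2, say whether aggregate means pooled over arms or coded group totals.
- In the report of this trial, state who, if anyone, saw events by arm at the one look held. If nobody did, do not describe that look as a between-arm safety check.

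The cost is a few sentences and a few hours of a monitor already in place. The downside is that one more person sees by-arm data, and that person also handles drug questions for individual patients, so knowledge of the split could color those decisions. Coding the arms reduces this risk but does not remove it.
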